### 2.3. Benefit/Risk Assessment

This is a healthy volunteer study and there is no direct benefit to study subjects. Identified and potential risks are described below.

More information about the known and expected benefits and risks and reasonably expected AEs with ALXN1840 may be found in the current edition of the IB.

#### 2.3.2. Potential Risks

### 2.3.2.1. Pregnancy Exposure

No studies of ALXN1840 have been conducted in pregnant women. Pregnant or breastfeeding subjects will be excluded from the clinical study. To avoid pregnancy, appropriate precautions will be taken for subjects of childbearing potential as required in Section 6.9. In the event of a pregnancy in a study subject, the subject will be discontinued from study drug (Section 7) and followed up in accordance with Section 10.4 (Appendix 4).

### 3. OBJECTIVES AND ENDPOINTS

The study objectives and corresponding endpoints are presented in Table 5.

Table 5: Study WTX101-HV-106 Objectives and Endpoints

Objectives	Endpoints		
Primary			
To evaluate the ALXN1840 PK in Japanese and non-Japanese healthy subjects			
Secondary			
To assess the safety and tolerability of ALXN1840 in Japanese and non-Japanese healthy subjects	Safety assessed by incidence of TEAEs and TESAEs, physical examination, vital sign measurements, clinical laboratory and ECG results		
Exploratory			
To assess dose-proportionality of ALXN1840 PK of the 15 mg and 60 mg doses within each cohort and with combined cohort data	• PK parameters for plasma total Mo ( $C_{max}$ , $AUC_t$ , and $AUC_{\infty}$ )		
To explore PD and biomarkers of ALXN1840 in Japanese and non-Japanese healthy subjects	Absolute and percent changes of plasma Cp and copper levels (total Cu, Cp, CpC and NCC)		
	The NCC level will be corrected for the amount of Cu bound to the TPC (NCC corrected ).		

Abbreviations:  $AUC_{\infty}$  = area under the plasma concentration versus time curve from zero to infinity;  $AUC_t$  = area under the plasma concentration versus time curve from time 0 to the last quantifiable concentration;  $C_{max}$  = maximum observed concentration; Cp = ceruloplasmin; CpC = ceruloplasmin-bound copper; Cu = copper; Cu = molybdenum; CpC = non-ceruloplasmin-bound copper; CpC = CpC =

### 4. STUDY DESIGN

# 4.1. Overall Design

This is a single-center, open-label, two-single-dose, two-period, parallel group study evaluating PK and safety of ALXN1840 in healthy subjects. Pharmacokinetic parameters will be calculated based on the measurement of plasma total Mo concentration. Approximately 24 healthy (12 Japanese and 12 non-Japanese), non-tobacco using, adult male and female subjects who complete the study screening assessments and meet all eligibility criteria will be enrolled to allow for minimum 20 subjects to complete the study (10 subjects in each cohort).

Cohort 1: Japanese subjects (defined as those subjects whose parents and grandparents are both Japanese and who have spent less than 5 years outside of Japan).

Cohort 2: Non-Japanese subjects

The study has a screening phase (Days -28 to -2), 2 Dosing Periods (Day -1 to Day 11 each), and an end-of-study (EOS) visit. After completing the screening phase, enrolled subjects will be admitted to an inpatient facility (CRU) on Day -1 for dosing on Day 1 in Dosing Period 1. Subjects will be readmitted to the CRU for Dosing Period 2 dosing 14 days (+2 days) after the 15 mg dose.

During Days 1 to 11 of both Dosing Period 1 and Dosing Period 2, subjects will remain at the CRU and have samples obtained for PK/PD assessment as well as safety evaluations performed according to the Schedule of Activities (Table 1 and Table 2). Subjects will be discharged 10 days after dosing within Period 1 and Period 2 following the 240-hour post-dose procedures, unless it is medically necessary to extend their confinement.

The subjects in each cohort will follow the dosing regimen as outlined in Table 6. Detailed dosing instructions are provided in Section 6.1.

**Table 6:** Study Drug Dosing Periods

Dosing Period 1	Subjects will receive a single dose of one 15 mg ALXN1840 EC tablet at Hour 0 on Day 1 of Period 1 following an overnight fast
Dosing Period 2	Subjects will receive a single dose of 4 × 15 mg (for a total of 60 mg) ALXN1840 EC tablets at Hour 0 on Day 1 of Period 2 following an overnight fast.

Abbreviation: EC = enteric-coated.

Subjects will return to the CRU 14 days (+ 2 days) after the 60 mg dose in Dosing Period 2 for the EOS visit with follow-up procedures, and to determine if any AE had occurred since the last study visit. If subjects withdraw from the study early, they will be seen and assessed by the Investigator or designee, whenever possible, to undergo the procedures associated with the EOS visit. Subjects may be replaced at the discretion of the Sponsor.

The planned study duration for each subject is approximately 56 days; up to 27 days for screening and approximately 29 days for dosing and follow-up.

The study will be conducted at a single site in the UK.

A Safety Review Committee may be used to evaluate the study data for subject safety and make recommendations on dose modification or termination of the study.

# 4.2. Scientific Rationale for Study Design

- This study is being conducted in healthy subjects and not in patients with WD so that the assessments are not confounded by disease activity, comorbidities, or concomitant medications.
- The inclusion and exclusion criteria for this study are consistent with typical Phase 1 clinical pharmacology studies for assessing impact of ethnicity on the medication of interest to minimize assignment bias.
- A two-period, parallel-group study design was adopted to control the variability within and between subjects.
- The washout time between the 2 ALXN1840 dosing periods will be at least 14 days, based on the estimated mean half-life for ALXN1840 of approximately 2 days previously reported in the bioavailability Studies WTX101-101 and WTX101-102, where healthy subjects took oral dose at 60 mg. Therefore, the 14-day washout time between the Period 1 and Period 2 doses is considered sufficient to eliminate, on average, approximately more than 99.2% of the plasma total Mo before the next dose is administered. The 14-day washout time after Period 2 dosing will also ensure that more than 99.2% of ALXN1840 has been eliminated at the subject's EOS visit.

### 4.3. Justification for Dose

This study is being conducted to support enrollment of Japanese patients with WD into the ongoing Phase 3 Study WTX101-301, which is evaluating ALXN1840 dose titration range from 15 mg once every other day to 60 mg daily. These doses have been studied in previously reported single dose (60 mg in healthy subjects; Studies WTX101-101 and WTX101-102) and multiple dose (15 to 60 mg daily in patients with WD; Study WTX101-201) clinical studies.

ALXN1840 at 60 mg single dose has been shown to be safe and well-tolerated in healthy male and female subjects in Phase 1 bioavailability Studies WTX101-101 and WTX101-102. The 15 to 60 mg/day dose range has also been demonstrated to be efficacious with favorable safety profile in treating patients with WD in the Phase 2 Study WTX101-201 (Weiss, 2017).

The selection of the 15 mg and 60 mg single doses proposed in this study are, therefore, rational and appropriate for this study.

# 4.4. End of Study Definition

A subject is considered to have completed the study if the subject has completed all periods of the study including the EOS visit.

Measurement of the primary endpoints will be completed after the last visit of the last subject in the study. The end of the study is defined as the last visit for the last subject.

### 5. STUDY POPULATION

Prospective approval of protocol deviations to recruitment and enrollment criteria, also known as protocol waivers or exemptions, is not permitted.

### 5.1. Inclusion Criteria

Subjects are eligible to be included in the study only if all of the following criteria apply:

### Age/Sex

1. Male or female subject must be 18 to 45 years of age, inclusive, at the time of signing the informed consent.

### Weight

2. Body weight  $\leq 80 \text{ kg}$  and BMI within the range  $18 - 25 \text{ kg/m}^2$ , inclusive, at screening.

### **Pregnancy**

3. Negative serum pregnancy test at screening and Day -1 for all women of childbearing potential.

### Contraception

4. Female subjects of childbearing potential, if heterosexually active, and male subjects, if heterosexually active and with a female spouse or partner of childbearing potential or a pregnant or breastfeeding spouse or partner, must be willing to follow protocol-specified contraception guidance starting at least one menstrual cycle before first study drug administration and continuing for up to 3 months after the end of systemic exposure of the study drug (ie, 3 months after EOS visit) (described in Section 6.9).

#### **Other Inclusion Criteria**

- 5. Adequate venous access in the left or right arm to allow collection of a number of blood samples.
- 6. Willing and able to fast per the study requirements.
- 7. Satisfactory medical assessment with no clinically significant or relevant abnormalities as determined by medical history, physical examination, vital signs, 12-lead ECG, and clinical laboratory evaluation (hematology, biochemistry, coagulation, and urinalysis) that are reasonably likely to interfere with the subject's participation in or ability to complete the study, or to potentially confound interpretation of study results, as assessed by the Investigator.

#### **Informed Consent**

8. Willing and able to give written informed consent as described in Section 10.1.3. (Appendix 1) which includes compliance with the requirements listed in the informed consent form (ICF) and in this protocol.

### **5.2.** Exclusion Criteria

Subjects are excluded from the study if any of the following criteria apply:

#### **Medical Conditions**

- 1. Current or recurrent/chronic disease (eg, cardiovascular, hematological, neurological, endocrine, immunological, rheumatological, renal, hepatic or GI or other conditions) that or could affect clinical assessments or clinical laboratory evaluations.
- 2. Current or relevant history of physical or psychiatric illness that are not stable or may require a change in treatment, use of prohibited therapies during the study or make the subject unlikely to fully comply with the requirements of the study or complete the study, or any condition that presents undue risk from the study drug or study procedures.
- 3. Any other significant disease or disorder which, in the opinion of the Investigator, may put the subject at risk.
- 4. History of malignancy with the exception of a nonmelanoma skin cancer or carcinoma *in-situ* of the cervix that has been treated with no evidence of recurrence within 5 years.
- 5. Positive test for hepatitis B surface antigen (HBsAg) or Human immunodeficiency virus antibody (HIV Ab) at screening.
- 6. Acute or chronic hepatitis C virus (HCV) infection (evidenced by detection of HCV antibody and confirmed by detection of HCV RNA).
- 7. History of hypersensitivity to ALXN1840 or its excipients or any significant allergic reaction (eg. anaphylaxis or angioedema) to any product (eg. food, pharmaceutical).

### **Prior/Concomitant Therapy**

- 8. Use of prescription medications (excluding oral contraceptives) within 14 days prior to dosing on Day 1, except with prior approval of Alexion.
- 9. Use of nonprescription/ over-the-counter medications including vitamins and dietary or herbal supplements, within 7 days prior to dosing on Day 1.

# **Prior/Concurrent Clinical Study Experience**

10. Participation (ie, last protocol-required study visit) in a clinical study within 90 days before initiation of dosing on Day 1.

### **Diagnostic Assessments**

- 11. Supine systolic blood pressure < 90 mmHg at screening
- 12. Serum ceruloplasmin (Cp) value outside of the normal range at screening.
- 13. Serum total Cu value outside of the normal range at screening.

- 14. Hemoglobin level below the lower limit of normal at screening.
- 15. Serum creatinine > upper limit of normal of the reference range of the testing laboratory at screening or on Day -1.
- 16. Alanine aminotransferase, AST or total bilirubin outside of normal range at screening.
- 17. Any clinically significant abnormal hematological parameters (per the Investigator's discretion).
- 18. Donated or lost 400 mL blood or more within the last 16 weeks preceding the first day of dosing.

#### **Other Exclusion Criteria**

- 19. Female subjects who are breastfeeding.
- 20. Prior exposure to ALXN1840.
- 21. Major surgery or hospitalization within 90 days prior to dosing on Day 1.
- 22. Use of tobacco in any form (eg, smoking or chewing) or other nicotine-containing products in any form (eg, gum, patch, electronic cigarettes) 6 months prior to the planned first day of dosing (Section 5.3.2).
- 23. History of illicit drug abuse, history of significant alcohol abuse within 1 year prior to the screening visit, or clinical evidence of substance and/or alcohol abuse within the 2 years before screening. Alcohol abuse is defined as regular weekly intake of more than 14 units (for both males and females), using the following NHS alcohol tracker http://www.nhs.uk/Tools/Pages/drinks-tracker.aspx.
- 24. Positive urine drug toxicology screen at screening or on Day -1.
- 25. Alcohol consumption within 48 hours prior to study drug administration or positive alcohol breath test at screening or on Day -1.

# 5.3. Lifestyle Considerations

### **5.3.1.** Meals and Dietary Restrictions

- Subjects are required to abstain from ingesting food containing poppy seeds within 24 hours prior to admission.
- No outside food or drink is permitted at the CRU. All meals and snacks will be provided. Subjects will receive standard meals and snacks at scheduled times during confinement.
- Subjects will be administered the dose of ALXN1840 following an overnight fast.

### 5.3.2. Caffeine, Alcohol, and Tobacco

Subjects will be required to abstain from:

• Ingesting caffeine- or xanthine-containing products (eg, coffee, tea, cola drinks, and chocolate) 24 hours before admission through discharge from the CRU, and 24 hours before each study outpatient/follow-up visit.

• Ingesting alcohol 48 hours before admission through discharge from the CRU, and 48 hours before each study outpatient/follow-up visit.

• Using tobacco in any form (eg, smoking or chewing) or other nicotine-containing products in any form (eg, gum, patch, electronic cigarettes) 6 months prior to the planned first day dosing through to the EOS visit.

### 5.3.3. Physical Activity

Subjects will be required to abstain from strenuous physical activity 48 hours prior to blood draws for clinical safety laboratory testing. Subjects should not start new physical training activities during the study until study completion (last visit).

# **5.4.** Screen Failures and Replacements

Screen failures are defined as subjects who signed consent to take part in the study but were not randomized. A minimal set of screen failure information is required to ensure transparent reporting of screen failure subjects to meet the Consolidated Standards of Reporting Trials (CONSORT) publishing requirements and to respond to queries from regulatory authorities. Minimal information includes demography, screen failure details, eligibility criteria, and any SAE.

Rescreening is not permitted where the cause is not deemed to be temporary. Subjects who initially failed due to temporary non-medically significant issues (eg, screening occurs outside the planned window) are eligible for rescreening once the cause has resolved.

### **5.4.1.** Criteria for Study Termination

The Investigator, competent authority, or Alexion may terminate the study for reasonable cause. Conditions that warrant termination of the study include, but are not limited to, the following:

- Discovery of an unexpected, serious, or unacceptable risk to subjects enrolled in the study
- Decision on the part of Alexion to suspend or discontinue testing, evaluation, or development of the study drug
- Failure of the Investigator to comply with the approved protocol, pertinent guidelines, and/or regulations
- Submission of knowingly false information from the Investigator to Alexion and/or regulatory authorities

### 6. STUDY DRUG

Study drug is defined as any investigational drug product(s), marketed product(s), or placebo, intended to be administered to a subject according to the protocol.

# 6.1. Study Drug Administered

The study drug composition and doses to be administered in this study are presented in Table 7.

**Table 7:** Study Drug Administered

Study Drug Name: ALX	N1840 (formerly WTX101)	
	artie to (remierly transcrip	
Dosage Formulation: EC to	EC tablets (15 mg)	
Unit Dose Strength/Dosage level: 15 m	15 mg tablet	
Route of Administration Oral		
Dosing Instructions: Stud	y drug will be administered as outlined in Table 6.	
	tudy medications will be taken with approximately 240 mL of water. ects will be instructed not to crush, split, or chew the study medication.	
Additional instructions are trans	N1840 will be provided in blisters with each tablet situated in one parent thermoform cavity. Each blister will be labeled as required per try requirement.	
1 ,	lent, Inc.	

Abbreviation: EC = enteric-coated.

Source: ALXN1840 Investigator's Brochure

The blistered study drug will be supplied to the Investigator's site, as bulk. The site's pharmacy will repackage the supplies into individual, labelled subject doses and perform Qualified Person certification of the repackaged product.

# 6.2. Packaging and labeling

The labelling of the study drug will be in compliance with Good Manufacturing Practice specifications, as described in The Rules Governing Medicinal Products in the European Union, Volume 4, Annex 13, Investigational Medicinal Products, and any other or local applicable regulations.

Sample label(s) will be submitted to the UK health authorities according to the submission requirements.

# 6.3. Preparation/Handling/Storage/Accountability

- The Investigator or designee must confirm appropriate temperature conditions have been maintained during transit for all study drug received and any discrepancies will be reported and resolved prior to use of the study drug.
- Only subjects enrolled in the study may receive study drug and only authorized site staff may supply or administer study drug. All study drug must be stored in a secure, environmentally controlled, and monitored (manual or automated) area in accordance with the labeled storage conditions with access limited to the Investigator and authorized site staff.

 The Investigator, or qualified designee, is responsible for study drug accountability, reconciliation, and record maintenance (ie, receipt, reconciliation, and final disposition records).

Additional instructions are provided in the pharmacy manual.

# 6.4. Measures to Minimize Bias: Randomization and Blinding

This is an open-label study.

Eligible subjects who meet all inclusion and no exclusion criteria will be assigned unique numbers for enrollment. In order to minimize selection bias in treatment assignment, subjects who are assigned subject numbers will have them assigned consecutively at the point of study drug dosing, in the same order as they have become eligible. Study subject numbers will not be reallocated once assigned.

In an effort to achieve balance between the number of males and females in Cohorts 1 and 2, the maximum split in either direction will be 60%:40%.

# 6.5. Study Drug Compliance

Study drug will be administered to subjects in a controlled setting under the supervision of the Investigator, or designee, thereby ensuring compliance with study drug administration. Study center personnel will ensure that all subjects are adequately informed about the specific study drug dosing regimen required for compliance with the study protocol

# 6.6. Dose Escalation to Dosing Period 2

The decision to escalate dosing from Dosing Period 1 to Dosing Period 2 will be made by the Investigator and/or Safety Review Committee as described in Table 8.

Table 8: Rules for Escalation from Period 1 to Period 2

Dosing Decision	Responsible	Data to be Reviewed	Documentation/Communication
	Party		Methods
Escalation from	Investigator	All available safety and	The Investigator will document the
Dosing Period 1	and the	tolerability a data up to 72 hours	decision in an email to the Sponsor. The
to Dosing	Sponsor	after 15 mg dose from a	email does not require the Sponsor's
Period 2.		minimum of 10 subjects in	response, unless there is disagreement
		Cohort 1.	with the Investigator's decision.

<sup>a Safety and tolerability data comprise the following: TEAEs, vital signs (temperature, blood pressure, pulse rate, respiratory rate), 12-lead ECGs, clinical laboratory variables (hematology, coagulation, biochemistry and urinalysis).

Abbreviations: ECG = electrocardiogram; TEAE = treatment-emergent adverse event.

# 6.7. Study Drug Stopping Rules

An individual subject will not receive the 60 mg dose of ALXN1840 in Dosing Period 2, if either of the following occurs:

• Subject experiences any Grade 3 (or higher) treatment-emergent adverse event (TEAE) considered to be related to study drug.

• Subject experiences any Grade 1 or 2 TEAE considered to be related to study drug that is considered a safety concern by the Safety Review Committee.

Dosing will be suspended for all subjects, if either of the follow occurs:

- Two or more subjects (among any of the 24 total subjects) experience a non-serious, Grade 3 TEAE considered to be related to study drug.
- One subject experiences a serious, Grade 3 (or higher) TEAE considered to be related to study drug.

In the event of suspension of dosing, continuation of the study will require a protocol amendment.

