## 8.4. Safety Review Committee

An ad-hoc Safety Review Committee must convene within 24 hours in the case of a possible treatment-emergent serious adverse event (TESAE) considered to be related to study drug or the withdrawal of subjects due to TEAEs considered to be related to study drug in order to determine whether any stopping rules apply and the impact on study continuation (see Section 6.6 and Section 6.7).

There is an option to have additional ad-hoc Safety Review Committee meetings to discuss urgent issues should the need arise. The membership roster and requirements for documenting meeting discussions and outcome will be outlined in the Safety Review Committee charter. Further internal or external experts may be consulted by the Safety Review Committee as necessary.

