#### A serious adverse event is defined as any untoward medical occurrence that, at any dose:

#### 1. Results in death

#### 2. Is life-threatening

The term 'life-threatening' in the definition of 'serious' refers to an event in which the subject was at risk of death at the time of the event. It does not refer to an event, which hypothetically might have caused death, if it were more severe

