#### 5. Is a congenital anomaly/birth defect

#### 6. Other situations:

- Medical or scientific judgment should be exercised in deciding whether SAE reporting is appropriate in other
  situations such as important medical events that may not be immediately life-threatening or result in death or
  hospitalization but may jeopardize the subject or may require medical or surgical intervention to prevent one
  of the other outcomes listed in the above definition. These events should usually be considered serious.
- Examples of such events include invasive or malignant cancers, intensive treatment in an emergency room or at home for allergic bronchospasm, blood dyscrasias or convulsions that do not result in hospitalization, or development of drug dependency or drug abuse.

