### **Assessment of Event Severity**

The Investigator will make an assessment of intensity for each AE and SAE reported during the study and assign it to 1 of the following categories from CTCAE v5.0, published 27 Nov 2017. Each CTCAE term is a Lowest Level Term per MedDRA. Each Lowest Level Term will be coded to a MedDRA Preferred Term:

- 1. Grade 1: Mild (asymptomatic or mild symptoms; clinical or diagnostic observations only; intervention not indicated)
- 2. Grade 2: Moderate (minimal, local or noninvasive intervention indicated; limiting age-appropriate instrumental activities of daily living [ADL])
- 3. Grade 3: Severe (severe or medically significant, but not immediately life-threatening; hospitalization or prolongation of hospitalization indicated; disabling; limiting self-care ADL)
- 4. Grade 4: Life-threatening consequences; urgent intervention indicated
- 5. Grade 5: Death related to AE

Any change in the severity of an AE should be documented based on specific guidelines in the CRF Completion Guidelines.

Severity and seriousness must be differentiated: severity describes the intensity of an AE, while the term seriousness refers to an AE that has met specific criteria for an SAE as described above.

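### The group-suspension rule for non-serious events names Grade 3 only, so a related non-serious Grade 4 event counts toward neither group trigger

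*Protocol*

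**What the plan says.** Protocol Section 6.7 sets three rules that depend on grade.

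- **Individual rule.** "An individual subject will not receive the 60 mg dose of ALXN1840 in Dosing Period 2" if "Subject experiences any Grade 3 (or higher) treatment-emergent adverse event (TEAE) considered to be related to study drug". A separate limb covers related Grade 1 or 2 events that worry the Safety Review Committee.
- **Group rule, non-serious events.** Dosing stops for all if at least two of the 24 subjects "experience a non-serious, Grade 3 TEAE considered to be related to study drug".
- **Group rule, serious events.** Dosing stops for all if "One subject experiences a serious, Grade 3 (or higher) TEAE considered to be related to study drug".

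After a group suspension the study can continue only under a protocol amendment.

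Three other parts of the protocol bear on how these rules work. Section 10.3.4 defines the top non-fatal grade as "Grade 4: Life-threatening consequences; urgent intervention indicated", and also requires severity and seriousness to be kept distinct. Section 10.3.2 makes an event serious on the life-threatening criterion only if the subject was actually at risk of death at the time: "It does not refer to an event, which hypothetically might have caused death, if it were more severe". For other important medical events, which are left to medical judgement, it says: "These events should usually be considered serious".

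**The concern.** Two of the three rules extend upward from Grade 3 and one does not. Because the qualifier appears on either side of it, the natural reading of the middle rule is Grade 3 exactly. Nothing else in the protocol or SAP extends it.

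The result is an ordering that makes no clinical sense: two related non-serious Grade 3 events suspend dosing, but a pair that includes a Grade 4 event does not. The subjects are healthy volunteers with no direct benefit (Section 2.3). An automatic stopping rule is there so that suspension does not depend on someone's judgement on the day, and for this combination it is silent.

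**Working it through.** The documents state no operating characteristic for the stopping rules, so there is no figure to reproduce. The check applies the rules literally and then with the wording changed.

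**Rules as written (Section 6.7), related events only**

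- (a) suspend if the number of subjects with a non-serious event of grade = 3 is at least 2
- (b) suspend if the number of subjects with a serious event of grade ≥ 3 is at least 1

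**Amended rule:** (a) uses grade ≥ 3; (b) is unchanged.

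| Related events, one per subject | As written | Amended |
|---|---|---|
| Non-serious 3 + non-serious 3 | suspend | suspend |
| Non-serious 3 + non-serious 4 | continue | suspend |
| Non-serious 4 + non-serious 4 | continue | suspend |
| Five non-serious Grade 4 | continue | suspend |
| One non-serious Grade 4 | continue | continue |
| One serious Grade 3 | suspend | suspend |
| One serious Grade 4 | suspend | suspend |

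Grade 5 is death, hence always serious, so the gap is Grade 4 only. Of the three possible non-serious pairs, 1 of 3 suspends as written and 3 of 3 as amended. This counts combinations; it is not a probability.

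**Can a Grade 4 event be non-serious under this protocol?** Yes, though seldom. Section 10.3.4 separates the two scales and Section 10.3.2 asks about actual risk of death. Laboratory values are graded with CTCAE as a guide (protocol Section 9.4.2; SAP Section 4.11.2), so a grade can rest largely on a number. The identified risks in Section 2.3.1 include asymptomatic aminotransferase rises, with ALT up to 1341 IU/L and no notable bilirubin increase. Those were in patients with Wilson disease, 4 to 10 weeks into daily dosing.

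**Does another provision fill the gap?**

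- The individual rule withholds that subject's own 60 mg dose. It protects no one else and has no effect once that dose has been given.
- The escalation review (Section 6.6, Table 8) requires data to 72 hours after the 15 mg dose from at least 10 Cohort 1 subjects. The scheduled chemistry at 96 and 216 hours (Table 2), and all of Period 2, fall outside that minimum.
- The Safety Review Committee must meet for a possible related serious event or for withdrawal of subjects due to related events (Section 8.4). Its task then includes deciding whether a stopping rule applies, and as written this one would not. Stopping drug (Section 7.1) is handled separately from leaving the study (Section 7.2), so a withheld dose need not count as a withdrawal.
- Medical-monitor discussion (Section 8), optional committee meetings (Section 8.4) and study termination (Section 5.4.1) lead to suspension only by judgement.

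**Scale, on assumed rates.** The documents give no rates for these events. Let p3 and p4 be the per-subject probabilities of a related non-serious event of Grade 3 and Grade 4, taken as mutually exclusive, with subjects independent and all 24 dosed. Then P(rule (a) is met) = 1 − (1 − p)^24 − 24p(1 − p)^23, with p = p3 as written and p = p3 + p4 as amended.

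| p3 | p4 | As written | Amended |
|---|---|---|---|
| 2% | 0.5% | 0.083 | 0.120 |
| 5% | 1% | 0.339 | 0.427 |
| 10% | 5% | 0.708 | 0.894 |

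These rates are for illustration and are probably too high: in the two earlier healthy-volunteer studies (18 subjects each), every adverse event was Grade 1 except one at Grade 2 (Section 2.2).

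**The case against.** The best reply is that the uncovered case is nearly empty. Grade 4 is defined by life-threatening consequences, life-threatening events are serious, and important medical events (blood dyscrasias are among the examples) are usually to be classed as serious. One related serious event of Grade 3 or more already suspends dosing for all. Laboratory grading uses CTCAE only as a guide alongside clinical judgement, so a Grade 4 label is not mechanical. A related Grade 4 event would also be hard to dismiss as not even a possible serious event while under assessment, so the committee would probably meet within 24 hours of the first one, without waiting for a second. Previous single doses of 60 mg were well tolerated, and Section 2.3.1 says drug effects appeared only after several weeks of daily dosing. After the 60 mg dose, the affected subject has no further dose to lose.

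Most of this stands, and it makes the practical risk small. It does not close the gap. A mandatory meeting is a review, not a suspension. Classifying such events as serious is usual, not required. And if every Grade 4 event really were serious, the extra words would do no harm.

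**Conclusion.** The concern holds. As written, a related non-serious Grade 4 event contributes to neither group trigger, and two of the three grade pairs that should suspend dosing do not. This is probably a drafting omission: the protocol gives no reason for limiting the rule to exactly Grade 3.

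The practical reach is narrow. It depends on an investigator grading an event 4, judging it related, and finding that no seriousness criterion is met, with a second subject having a related non-serious event of Grade 3 or 4. It also assumes that some subjects still have a dose to come when the second event is known; the documents describe no dosing stagger, so this cannot be checked. It should be corrected because it is a safety decision threshold, not because a failure is expected.

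**What to change.** In Section 6.7, in the first bullet on suspending dosing for all subjects, insert *(or higher)* immediately after *Grade 3*. Leave the other bullets as they are. The three rules then use the same lower bound, and any two subjects with related non-serious events of Grade 3 or 4 suspend dosing.

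The cost is two words at the next amendment and a slightly greater chance of a suspension, after which continuing requires a protocol amendment. The sponsor already accepts that consequence for the milder pair. Endpoints, analysis and sample size do not change.
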